9.4 Vital Sign Data

For each vital sign parameter (by position for blood pressure and pulse rate), descriptive statistics of actual measurements and changes from baseline at each time point and the last assessment time point will be calculated for each treatment group and for the overall brexpiprazole group.

Numbers and proportions of subjects with vital signs meeting the criteria for potentially clinically significant vital signs (Appendix 1) will be determined for each treatment group and for the overall brexpiprazole group. A listing of these subjects will be provided.

For each vital sign parameter in the antidepressant treatment period (Phase A), descriptive statistics of actual measurements and changes from baseline (before the start of the antidepressant treatment period [Phase A]) at each time point and the last assessment time point will be calculated overall and for each requisite concomitant medication in the ADT set. A listing of subjects with vital signs meeting the criteria for potentially clinically significant vital signs (Appendix 1) will be provided.

For each vital sign parameter in the antidepressant treatment period (Phase A) and the antidepressant-responder treatment-continuation period (Phase A+), descriptive statistics of actual measurements and changes from baseline (before the start of the antidepressant treatment period [Phase A]) at each time point and the last assessment time point will be calculated overall and for each requisite concomitant medication in the Phase A+ set. A listing of subjects with vital signs meeting the criteria for potentially clinically significant vital signs (Appendix 1) will be provided.

9.5 Physical Examination Data

Physical examination data will be provided in a listing.

9.6 Electrocardiogram Data

For heart rate, PR interval, RR interval, QRS interval, QT interval, and QT corrected for heart rate (QTc), descriptive statistics of actual measurements and changes from baseline at each time point and the last time point will be calculated for each treatment group and for the overall brexpiprazole group.

A shift table from baseline for normal/abnormal 12-lead electrocardiogram (ECG) (evaluated at the trial site) will be produced for each treatment group and for the overall brexpiprazole group.

Numbers and proportions of subjects with actual measurements of QTc (QTcF, QTcB, QTcN) not meeting the criteria of > 450 msec, > 480 msec, and > 500 msec at baseline and meeting the criteria after treatment will be determined for each treatment group and for the overall brexpiprazole group. Numbers and proportions of subjects with actual measurements of > 450 msec with a % change from baseline of $> 10\%$ will be determined for each treatment group and for the overall brexpiprazole group.

Numbers and proportions of subjects with ECG results meeting the criteria for potentially clinically significant ECG data (Appendix 3) will be determined for each treatment group and for the overall brexpiprazole group. A listing of these subjects will be provided.

For each ECG parameter in the antidepressant treatment period (Phase A), descriptive statistics of actual measurements and changes from baseline (before the start of the antidepressant treatment period [Phase A]) at each time point and the last assessment time point will be calculated overall and for each requisite concomitant medication in the ADT set. A listing of subjects with ECG results meeting the criteria for potentially clinically significant ECG data (Appendix 3) will be provided.

For each ECG parameter in the antidepressant treatment period (Phase A) and the antidepressant-responder treatment-continuation period (Phase A+), descriptive statistics of actual measurements and changes from baseline (before the start of the antidepressant treatment period [Phase A]) at each time point and the last assessment time point will be calculated overall and for each requisite concomitant medication in the Phase A+ set. A listing of subjects with ECG results meeting the criteria for potentially clinically significant ECG data (Appendix 3) will be provided.

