| 20 | Patients with a history of neuroleptic malignant syndrome or serotonin syndrome | | | | | | | | |
| 21 | Patients with a history or complication of epilepsy or epileptic seizures, excluding pediatric febrile seizures, post-traumatic seizures, alcohol withdrawal seizures, and other seizures | | | | | | | | |
| 22 | Patients with the following clinical laboratory test values or ECG parameters at screening (assessed based on results from the central laboratory and central ECG measurement facility) | | | | | | | | |
| | a) Platelet count: $\leq 75,000/\text{mm}^3$ | | | | | | | | |
| | b) Hemoglobin: ≤ 9 g/dL | | | | | | | | |
| | c) Absolute neutrophil count: ≤ 1000/mm ³ | | | | | | | | |
| | d) Aspartate aminotransferase (AST): > 2 times the upper limit of the reference range | | | | | | | | |
| | e) Alanine aminotransferase (ALT): > 2 times the upper limit of the reference range | | | | | | | | |
| | f) Creatine phosphokinase (CPK): > 3 times the upper limit of the reference range | | | | | | | | |
| | g) Creatinine: ≥ 2 mg/dL | | | | | | | | |
| | h) QT interval as corrected by Fridericia's formula (QTcF): ≥ 450 msec | | | | | | | | |
| 23 | Patients with a history of hypersensitivity to antidepressants | | | | | | | | |
| 24 | Patients with a history or complication of allergy to more than one medication | | | | | | | | |
| 25 | The following patients falling under the contraindications in the package insert for brexpiprazole | | | | | | | | |
| | tablet | | | | | | | | |
| | a) Patients in a coma | | | | | | | | |
| | b) Patients under the strong influence of central nervous system depressants including barbiturate analogs/anesthetics | | | | | | | | |
| | c) Patients receiving adrenaline | | | | | | | | |
| | d) Patients with a history of hypersensitivity to components of brexpiprazole tablet | | | | | | | | |
| 26 | Patients who otherwise should not participate in the trial in the opinion of the investigator or subinvestigator | | | | | | | | |
| At the | e initiation of the antidepressant treatment period (Phase A) | | | | | | | | |
| 27 | Pregnant or breastfeeding female subjects, or those with positive pregnancy test (urine) results at th initiation of the antidepressant treatment period (Phase A) | e | | | | | | | |
| 28 | Subjects newly requiring hospitalization for the current major depressive episode during the | | | | | | | | |

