At the initiation and Week 8 (or discontinuation) of the antidepressant treatment period (Phase A), Week 6 (or discontinuation) of the double-blind period (Phase B), and Week 6 (or discontinuation) of the antidepressant-responder treatment-continuation period (Phase A+)

(b) Methods

Measurement will be performed while the subject is minimally clothed (lightly clothed, removing heavy outer garments). The top of the hip bone and the upper edge of the right iliac crest will be located, and then a measuring tape will be placed horizontally all the way around the abdomen at the height of the iliac crest. Prior to measurement, the person engaged in measurement should ensure that the measuring tape is snug without indenting the subject's skin and is parallel to the floor. At the end of a normal expiration, waist circumference will be measured in centimeters (rounded off to the nearest whole number) and the date and result of measurement will be recorded in the source documents and the CRF.

(4) Height and body weight

(a) Time points

At screening, Week 8 (or discontinuation) of the antidepressant treatment period (Phase A), Week 6 (or discontinuation) of the double-blind period (Phase B), and Week 6 (or discontinuation) of the antidepressant-responder treatment-continuation period (Phase A+)

However, height will be measured only at screening.

(b) Methods

Body weight and height will be measured at the specified time points, and the date and results of measurement will be recorded in the source documents and the CRF (body weight in increments of 0.1 kg, height in increments of 0.1 cm). Body weight will be measured by the standard measurement method (fully clothed but without shoes) using a reliable, calibrated scale (the same scale should always be used to measure a particular subject).

3.7.3.4 12-lead Electrocardiography

(1) Time points

At screening, Week 8 (or discontinuation) of the antidepressant treatment period (Phase A), Week 6 (or discontinuation) of the double-blind period (Phase B), and Week 6 (or discontinuation) of the antidepressant-responder treatment-continuation period (Phase A+)

(2) Methods

The investigator or subinvestigator will record the subject's ECG using a 12-lead electrocardiograph supplied by the central ECG laboratory, assess whether the ECG

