result is normal or abnormal, and record the date and time of ECG, normal/abnormal judgement, and abnormal findings in the source documents and the CRF. The original of the 12-lead ECG chart will be kept in the medical record or the investigator's file. The central ECG laboratory will collect 12-lead ECG data and measure heart rate, PR interval, RR interval, QRS interval, QT interval, and QT corrected for heart rate (QTc) [QTcB = QT interval/(RR interval)^{1/2}, QTcF = QT interval/(RR interval)^{1/3}, QTcN = QT interval/(RR interval)^{0.37}], and the physician of the central ECG laboratory will assess the data. The central ECG laboratory will report the results of analysis to the investigator or subinvestigator. The investigator or subinvestigator will confirm the results of analysis and date and sign the analysis result report to make it an official document. The investigator or subinvestigator will reconfirm the normal/abnormal judgement with reference to the analysis result report sent from the central ECG laboratory. The results of analysis, which will be reported directly from the central ECG laboratory to the sponsor as an electronic file, do not need to be recorded in the source documents or the CRF.

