7.6.4 Electrocardiogram Data

For heart rate, PR interval, RR interval, QRS interval, QT interval, and QTc, descriptive statistics of actual measurements and changes from baseline at each time point will be calculated for each treatment group and for the overall brexpiprazole group.

A shift table from baseline for normal/abnormal 12-lead ECG will be produced for each treatment group and for the overall brexpiprazole group.

Numbers and proportions of subjects with actual measurements of corrected QT interval (QTcF, QTcB, QTcN) at each time point of > 450 msec, > 480 msec, and > 500 msec will be determined for each treatment group and for the overall brexpiprazole group. Numbers and proportions of subjects with changes from baseline of > 30 msec and > 60 msec will be determined for each treatment group and for the overall brexpiprazole group.

Numbers and proportions of subjects with ECG results meeting the criteria for potentially clinically significant ECG data will be determined for each treatment group and for the overall brexpiprazole group.

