The mean plasma brexpiprazole concentration over time and individual values at each time point after the most recent dosing will be plotted by treatment group. Plotted diagrams by CYP2D6 phenotype in each treatment group and by requisite concomitant medication in each treatment group will also be provided in the same manner.

Scatter plots of plasma brexpiprazole concentrations over time will be provided by treatment group. Scatter plots by CYP2D6 phenotype in each treatment group and by requisite concomitant medication in each treatment group will also be provided in the same manner.

Plasma brexpiprazole concentrations below the lower limit of quantitation will be handled as 0 (ng/mL) when their descriptive statistics are calculated and when plotted diagrams and scatter plots are created.

11 Pharmacodynamic Analyses

Not applicable.

12 Pharmacogenomic Analyses

CYP2D6 genotype (phenotype) will be tabulated as specified in [Section 7.2 Demographic and Baseline Characteristics](#). CYP2D6 phenotype will also be summarized in subgroup efficacy and safety analyses.

13 Interim Analysis

No interim analyses are planned.

14 Changes in the Planned Analyses

- The following changes were made to categorical analyses of QTc:
Only subjects with postdose QTc meeting the criteria will be summarized, instead of summarization at all time points.

Only subjects with QTc not meeting the criteria at baseline and meeting the criteria after baseline will be summarized.
- It has been decided that CYP2D6 phenotype will be tabulated as specified in [Section 7.2 Demographic and Baseline Characteristics](#). CYP2D6 phenotype will also be summarized in subgroup efficacy and safety analyses.
- The original plan of using the LOCF dataset in ANCOVA of safety endpoints was changed as follows: Measurements at each time point and at the last assessment time point and, as necessary, the worst postdose measurement will be included in the analysis.
- The original plan of calculating descriptive statistics of plasma brexpiprazole concentrations by treatment group in pharmacokinetic analysis was changed as follows: Descriptive statistics of plasma brexpiprazole concentrations at each time point after the most recent dosing, trough concentrations, and plasma drug concentrations at all time points will be calculated by treatment group, by CYP2D6 phenotype in each treatment group, and by requisite concomitant medication in each treatment group.

15 References

Not applicable.

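### SAP 9.6 omits the protocol's counts of QTc changes above 30 and 60 msec and adds a new QTc rule; SAP Section 14 records neither

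*SAP*

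**What the plan says.** Protocol 7.6.4 sets out two kinds of categorical QTc analysis. The first counts subjects above 450, 480 and 500 msec at each time point on QTcF, QTcB and QTcN. The second is a separate sentence on size of change: numbers and proportions of "subjects with changes from baseline of > 30 msec and > 60 msec will be determined", by treatment group and for brexpiprazole overall.

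SAP 9.6 has three QTc categories:

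- subjects newly above 450, 480 or 500 msec, that is, not above at baseline but above after treatment, on each of the three corrections;
- subjects above 450 "msec with a % change from baseline of" more than 10%, which has no counterpart in the protocol;
- subjects meeting SAP Appendix 3, whose only QTc entry is QTcF above 450 msec, with the change column left blank.

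None of these counts subjects by the absolute size of the QTc change.

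SAP Section 14 has an item on the categorical QTc analyses. It declares two changes: "Only subjects with postdose QTc meeting the criteria will be summarized, instead of summarization at all time points", and "Only subjects with QTc not meeting the criteria at baseline and meeting the criteria after baseline will be summarized". It does not mention the loss of the 30 and 60 msec counts or the added 10% rule. SAP Appendix 5 lists table CT-12.3 under a title about categorical QT/QTc changes, but only the title is given, and SAP 9.6 defines no absolute-change category to put in it.

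**The concern.** A safety count planned in the protocol has gone from the SAP, and the section meant to record such departures does not show it. The 10% rule occupies the place of the change counts and could be taken for their replacement, so it matters whether it does the same work.

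The SAP treats QT prolongation as an adverse event of interest (SAP 9.2.1). What is lost is the between-group comparison of how many subjects had a QTc change of a given size. Threshold counts do not supply it. A subject who moves from 380 to 445 msec crosses no threshold on that correction. A subject who moves from 390 to 451 msec is counted as crossing 450, not as having risen by more than 60.

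**Working it through.** The plan gives no figure of its own to reproduce here. The check is what each SAP 9.6 category can and cannot capture. Write b for baseline, p for the post-dose value and d = p − b, in msec, for one correction.

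**1. What every category requires.** Newly above 450, 480 or 500 needs p > 450 at least. The 10% rule needs p > 450. Appendix 3 needs QTcF p > 450. So p ≤ 450 enters none of them, and the rise needed to enter any category from a baseline at or below 450 is more than 450 − b:

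| Baseline | Rise must exceed |
|---|---|
| 360 | 90 |
| 380 | 70 |
| 390 | 60 |
| 400 | 50 |
| 420 | 30 |

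A rise above 60 can therefore end at or below 450 when b < 390, and a rise above 30 when b < 420.

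**2. Enumeration.** Over whole-msec baselines of 330 to 450 (an assumed range) with p ≤ 450, there are 60 × 61 / 2 = 1830 pairs with d > 60 and 90 × 91 / 2 = 4095 pairs with d > 30. None enters any SAP 9.6 category for that correction. Examples: 380 to 445 (+65, 17.1%) and 389 to 450 (+61, 15.7%) enter none. By contrast, 390 to 451 (+61, 15.6%) enters newly above 450, the 10% rule and, for QTcF, Appendix 3.

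**3. Can the 10% rule stand in for the change counts?** It needs b + d > 450 and d > 0.10b, so 450 − d < b < 10d. This has a solution only if 11d > 450, that is d > 450 / 11 = 40.9. A rise of 40.9 msec or less can never be flagged.

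**4. Does it add subjects to the newly-met counts?** If each threshold is judged separately:

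- b ≤ 450: p > 450 is already newly above 450.
- 450 < b ≤ 480: p > 1.1 × 450 = 495, already newly above 480.
- 480 < b ≤ 500: p > 1.1 × 480 = 528, already newly above 500.

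It adds a subject only when b > 500. Exclusion criterion 22 h bars "formula (QTcF): ≥ 450 msec" at screening, so for QTcF that needs a rise of more than 50 msec between screening and the Phase B baseline.

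**5. Other corrections.** From the formulas in Protocol 3.7.3.4, with heart rate HR = 60/RR, QTcB = QTcF × (HR/60)^(1/6) and QTcN = QTcF × (HR/60)^0.0367.

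- QTcF 380 to 445 has QTcB above 450 at a Week 6 heart rate above 60 × (450/445)^6 = 64.2 bpm, and is then counted if baseline QTcB was not already above 450.
- QTcF 360 to 425 (+65) stays at or below 450 on all three corrections up to 60 × (450/425)^6 = 84.5 bpm, and 385 to 420 (+35) up to 60 × (450/420)^6 = 90.8 bpm. These rises are in no category at all.

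**The case against.** The strongest reply is that little information is lost. SAP 9.6 still gives descriptive statistics of QTc change, and SAP 7.2 defines these to include the maximum. It also says "A shift table from baseline for normal/abnormal 12-lead electrocardiogram (ECG) (evaluated at the trial site) will be produced". QT-prolongation adverse events are tabulated (CT-8.9.14) and every ECG result is listed (PDATA-9.1). Phase B schedules one post-baseline ECG, at "Week 6 (or discontinuation) of the double-blind period (Phase B"), so if a group's maximum change on that ECG is 60 msec or less, its count above 60 is zero. The overseas depression trials report no marked ECG changes on brexpiprazole (Protocol 1.2.2.1 to 1.2.2.3), so large rises may be few. All of this stands and limits the weight of the point. But a maximum is not a count, the shift table is a site judgement of normal or abnormal, and where the maximum exceeds the threshold no planned table gives the number, although it could be programmed from the data collected.

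Three stronger readings are tempting and not supported.

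- *That these subjects escape every category, with a limit on Week 6 QTcF and heart rate deciding who.* Another correction may catch the subject, and baseline heart rate matters too, because the main counts need the threshold to be newly met. Take baseline QTcF 415 at 100 bpm (QTcB 451.9) and Week 6 QTcF 447 at 65 bpm (QTcB 453.0, QTcN 448.3). QTcF rises 32 msec and no category is entered: QTcB was already above 450 and changes by only 0.2%. Yet 447 lies above the limit 450/(65/60)^(1/6) = 444.0. Limits of this kind, and the step 5 examples, are sufficient for escape but not necessary; shares of subjects built on them would be lower bounds.
- *That the 10% rule is always redundant.* The SAP wording can also be read as excluding from the new counts anyone above 450 at baseline. On that reading the rule does add subjects with baselines between 450 and 500.
- *That the counts were deliberately removed.* CT-12.3 shows only its title, so the documents establish an unrecorded mismatch, not an intention.

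**Conclusion.** The point holds as a protocol–SAP mismatch in a descriptive safety table that should be reconciled. The 30 and 60 msec counts are in the protocol and not in SAP 9.6, Appendix 3 or any defined content of CT-12.3. The 10% rule is new and is no substitute, and SAP Section 14 is silent on both. The per-correction gap (baselines below 390 for a rise above 60, below 420 for a rise above 30) follows from the category definitions and needs no outside assumption. The redundancy result in step 4 rests on judging each threshold separately.

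How many subjects would be affected cannot be derived: the documents give no baseline QTc distribution, no heart rates and no frequency of such rises. The size is therefore stated only as the rise needed at each baseline. The primary analysis and the error control are not touched.

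**What to change.** In SAP 9.6 and table CT-12.3, restore the numbers and proportions of subjects with post-baseline QTc changes of more than 30 and more than 60 msec, for QTcF, QTcB and QTcN, by treatment group and for brexpiprazole overall. Protocol 7.6.4 speaks of changes, not increases, and names the three corrections only in the preceding sentence. The restored text should state the direction and the corrections explicitly. The 10% rule may stay as an addition, but Section 14 should list it. SAP 9.6 should also say whether the newly-met thresholds are judged separately or jointly. If dropping the change counts is intended, Section 14 should record that with the reason.

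The cost is two rows for each of three corrections (six rows) in an existing table, a sentence or so in SAP 9.6 and one line in Section 14. The data are already collected.

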9.7 Other Safety Data

9.7.1 Body Weight, BMI, and Waist Circumference

For body weight, BMI, and waist circumference, descriptive statistics of actual measurements and changes from baseline at each time point and the last assessment time point will be calculated for each treatment group and for the overall brexpiprazole group.

In addition, analysis will be performed by the ANCOVA model with treatment group as a factor and baseline as a covariate. Least square means of each treatment group and differences in least square means between each brexpiprazole group and the placebo group, as well as the two-sided 95% CIs will be determined.

Numbers and proportions of subjects with results meeting the criteria for potentially clinically significant body weight gain or loss (Appendix 1) will be determined for each treatment group and for the overall brexpiprazole group. Body weight data will also be analyzed by baseline BMI category (< 18.5 , ≥ 18.5 to < 25 , ≥ 25 to < 30 , ≥ 30) in a similar manner. A listing of subjects with results meeting the criteria for potentially clinically significant body weight gain or loss (Appendix 1) will be provided.

For body weight, BMI, and waist circumference in the antidepressant treatment period (Phase A), descriptive statistics of actual measurements and changes from baseline (before the start of the antidepressant treatment period [Phase A]) at each time point and the last assessment time point will be calculated overall and for each requisite concomitant medication in the ADT set. A listing of subjects with results meeting the criteria for potentially clinically significant body weight gain or loss (Appendix 1) will be provided.

For body weight, BMI, and waist circumference in the antidepressant treatment period (Phase A) and the antidepressant-responder treatment-continuation period (Phase A+), descriptive statistics of actual measurements and changes from baseline (before the start of the antidepressant treatment period [Phase A]) at each time point and the last assessment time point will be calculated overall and for each requisite concomitant medication in the Phase A+ set. A listing of subjects with results meeting the criteria for potentially clinically significant body weight gain or loss (Appendix 1) will be provided.

